733 *Counseling.* As in our prior work ([name] et al., 2012), participants will receive brief individual  
 734 behavioral counseling at 6 clinic visits (Weeks -4, -3, -1, 0 [TQD], 2, and 4) from counselors blind to  
 735 treatment group. Pre-quit sessions focus on topics common in behavioral counseling, including honing the  
 736 motivation to quit, identification of smoking triggers and trigger management, and social support (e.g.,  
 737 Abrams & Niaura, 2003; Fiore et al., 2008), without explicitly discussing extinction. However, to allow  
 738 extinction to occur, we will not include active nicotine fading as part of the counseling. Instead, participants  
 739 will be asked to follow their smoking urges, smoking at least 25% of their baseline rate to allow their  
 740 bodies time to adjust to the medication, as in prior extended pre-quit work ([name] et al., 2012, 2015; Rose  
 741 et al., 1998). In response to feedback from participants in prior studies, we will also offer brief counseling  
 742 "check-ins" by phone 1 and 7 weeks post-TQD.

743  App10-03a-EVQ2 Counseling SOP 2017-09-21.docx provides the Counselor Manual and App10-03b-  
 744 EVQ2 Counseling Handouts 2017-09-21.docx provides the participant workbook.

745 *End-Of-Treatment (EOT) and 6-months post-TQD (6M) visits* allow for biochemical verification  
 746 of self-reported abstinence, the primary outcome measure. Retention has been strong in our prior  
 747 varenicline studies ([name] et al., 2012; Lerman et al., 2015). Clear explanations of the importance of

748 follow-up data for clinical application, ongoing contact with participants (including reminder calls), and  
 749 increased remuneration for attendance at EOT and 6M visits (when medication is no longer being provided)  
 750 bolster retention, which is expected to be 95% at TQD, 82% at EOT, and ~75% at 6M (based on [name] et  
 751 al., 2012 and the Buffalo varenicline arm data from Lerman et al, 2015).

752 **Update 2019-11:** Retention at EOT and 6M follow-up has been substantially lower than anticipated. We  
 753 believe this is related to several inter-related factors. First, because of the EMA remuneration (up to  
 754 \$35/week), remuneration at Clinic Visits is much higher than in our prior studies. Second, remuneration at  
 755 EOT and 6M is actually somewhat lower than in our prior work – we did this in an effort to stay under the  

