 756 \$600 threshold at which a 1099 would have to be issued, requiring participants to provide us with their  
 757 SSN. We now re-balance the remuneration by shifting some remuneration from Clinic visits (which already  
 758 have greater value because of the treatment received and the EMA remuneration) to the follow-up period  
 759 (see Section 26).

760 In addition, we have observed that many participants do not answer the reminder calls for follow-  
 761 up visits, and when they do not answer the phone call they are very likely (70-90%) to miss the subsequent  
 762 follow-up. After extensive discussion with staff, and consideration of anecdotal information from  
 763 participants, we will replace the reminder calls with brief (1-2 questions) REDCap surveys (see App 11.1 –  
 764 Template for REDCap Follow-Up Survey) delivered via a text message link to the participant's phone. We  
 765 have designed a plan we believe offers multiple advantages:

766 1) Rather than requiring that a participant answer our phone call at a specific time, participants can respond  
 767 to a REDCap survey whenever they are available. Because participants have already completed 9 weeks of  
 768 electronic assessments, this should be convenient and low-burden.

769 2) REDCap allows us to automate reminders to participants' who do not respond to the initial text of a  
 770 survey link. We will send up to 3 reminders for each survey.

771 3) In contrast to phone calls, which could be associated with shame or embarrassment for participants who  
 772 report relapsing to smoking, the REDCap surveys allow participants to report electronically without direct  
 773 mention of the behavior to study staff.

774 4) Because the surveys are so brief, we can actually have more frequent contact with participants during the  
 775 follow-up period (1, 3, and 5 weeks before EOT and 4 and 8 weeks before 6M follow-up), which should  
 776 enhance retention rates.

777 *Participant Satisfaction Surveys (C4 and EOT)* Participants will be given satisfaction surveys at  
 778 Clinic visit #4 (C4) and the End of treatment (EOT) visits. These surveys will be distributed in an unsealed  
 779 enveloped. The participant will be asked to complete the survey on paper, in private, to answer honestly,  
 780 and to seal the survey into the envelope after completion. Surveys will be delivered to [name]; research  

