 1314 thereby allowing adjustments to treatment to prevent patients from experiencing a failed quit attempt (e.g.,  
 1315 Rose et al., 2013) and providing precise targets to further enhance treatment effectiveness.

1316 *Aim 3.* We hypothesize that changes in pre-quit smoking behavior (i.e., percent reduction in CPD during  
 1317 the pre-quit period) will mediate the effect of extended pre-quit varenicline on smoking cessation. This aim  
 1318 will be tested with a path model whereby treatment will predict pre-quit reduction in smoking (a continuous

1319 variable), which in turn, will predict smoking abstinence. Separate models will be estimated for abstinence  
 1320 at EOT and 6M follow-up. Baseline levels of smoking will be included as a statistical control variable.  
 1321 Bootstrapped indirect effects with asymmetrical confidence bands will be used to test the proposed  
 1322 mediational path (MacKinnon 2008). We will also evaluate whether gender moderates this mediated path  
 1323 (moderated mediation, Preacher et al., 2007).

1324 **17.2 If applicable, provide a power analysis.**

1325 *NOTE: This may not apply to certain types of studies, including chart/records reviews, survey*  
 1326 *studies, or observational studies. This question is asked to elicit whether the investigator has an*  
 1327 *adequate sample size to achieve the study objectives and justify a conclusion.*

1328 Response: Although our analyses will utilize methods to handle missing data (e.g., full-information  
 1329 likelihood estimation; Enders & Bandalos, 2001), we conservatively estimated power based on N=320 ITT  
 1330 participants and attrition estimated to be 5% at TQD, 18% at EOT, and 25% at 6-M (based on our  
 1331 varenicline data from [name] et al., 2012 and Lerman et al., 2015). Our power estimates are based on an  
 1332 alpha level of .05 and adequate power considered  $\geq .80$ . For the main effects of treatment run-in group on  
 1333 outcome (Aim 1) and hypothesized mediators (Aim 2), power was computed using Proc Power in SAS  
 1334 based on effect size estimates from [name] et al. (2012) and Hajek et al. (2011); treatment run-in group  
 1335 effect sizes are expected to be in the range of small to medium for Aim 1 (Odds ratios 1.3 to 2.3) and Aim 2  
 1336 ( $f^2$  .05 to .12). Our proposed sample will provide adequate power to detect these effects. For gender  

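### Section 17.2 still bases its end-of-treatment and 6-month abstinence power on 18% and 25% attrition, although section 10.1 reports that retention at those visits fell well short

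*Combined protocol and SAP*

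**What the plan says.** Section 17.2 starts from 320 intent-to-treat "participants and attrition estimated to be 5% at TQD, 18% at EOT, and 25% at 6-M (based on our" investigators' earlier varenicline data. The standard is "alpha level of .05 and adequate power considered" to be at least .80. Aim 1 odds ratios are expected to lie between 1.3 and 2.3, Aim 2 effects between f² = .05 and .12, and power is called adequate throughout. No numeric power is printed, and the parameters of the Monte Carlo runs (gender interactions and Aim 3) are not given.

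Section 10.1 gives the same inputs as retention, "which is expected to be 95% at TQD, 82% at EOT, and ~75% at 6M". The 2019-11 update that follows reports: "Retention at EOT and 6M follow-up has been substantially lower than anticipated". It gives no observed rate and does not mention retention at the target quit date (TQD). It then describes two remedies: "We now re-balance the remuneration by shifting some remuneration from Clinic visits" to the follow-up period, and text-message surveys in place of reminder calls. Section 17.2 carries no corresponding update.

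**The concern.** EOT and 6M are the visits at which self-reported abstinence is biochemically verified. Aim 1 tests abstinence at both, and Aim 3 fits a separate mediation model for each. If losses exceed 18% and 25%, fewer outcomes are observed than the power calculation assumed, and the stated power for these analyses is too favourable. A null result, particularly at 6M, could then be read as better evidence of no benefit than the data can supply.

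The two sections conflict in current text. Elsewhere the protocol does correct a missed projection: section 5.2 replaces the predicted 10% loss before treatment starts with the observed 21%. Section 17.2 had no such correction.

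**Working it through.** **Inputs.** N = 320 randomised 1:1; losses of 5% (TQD), 18% (EOT) and 25% (6M); odds ratio (OR) up to 2.3; alpha .05; target power .80 (all section 17.2 except the allocation, section 10.1). Assumptions: alpha is two-sided. Control abstinence is 25% at 6M, from the one-in-four long-term rate in section 3.1, with 20-30% as sensitivity. At EOT the documents give no rate, so 30-50% is used.

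**Step 1: the plan's own N.** Outcome-complete N = 320 × (1 − loss):
- TQD: 320 × .95 = 304
- EOT: 320 × .82 = 262
- 6M: 320 × .75 = 240

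**Step 2: power at the plan's own inputs.** The treated rate is p₂ = p₁·OR / (1 − p₁ + p₁·OR). With n per arm and p̄ the mean of the two rates, power = Φ{ [ |p₂ − p₁|·√n − 1.96·√(2p̄(1 − p̄)) ] / √(p₁(1 − p₁) + p₂(1 − p₂)) }.

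For 6M: p₁ = .25 and OR 2.3 give p₂ = .575/1.325 = .434. With n = 120 per arm, power is .86. At EOT, n = 131 per arm and control 30-50% give .91-.92. Adequacy at OR 2.3 is therefore reproduced. It is not reproduced at OR 1.3, where power is about .17-.18 at EOT and .15 at 6M.

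**Step 3: higher losses.** The documents give no observed rate, so these rows are illustrations, not estimates.

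| Loss | N | EOT, control 30-50%: power at OR 2.3 | EOT: smallest OR with .80 power | 6M, control 25%: power at OR 2.3 | 6M: smallest OR with .80 power |
|---|---|---|---|---|---|
| 18% | 262 | .91-.92 | 2.0-2.05 | – | – |
| 25% | 240 | .88-.89 | 2.1 | .86 | 2.2 |
| 30% | 224 | .86-.87 | 2.1-2.2 | .83 | 2.2 |
| 35% | 208 | .83-.85 | 2.2 | .80 | 2.3 |
| 40% | 192 | .80-.82 | 2.3 | .77 | 2.4 |
| 45% | 176 | .76-.78 | 2.3-2.4 | .73 | 2.5 |

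The 6M result depends on the control rate. At OR 2.3, power at 35% loss is .76 for control 20% and .83 for control 30%. The N needed for .80 is 232, 208 and 194 at control 20%, 25% and 30%, so the loss at which power falls below .80 is 27.5%, 35% and 39%.

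**Step 4: what does not move.** The primary mediator is the percent reduction in cigarettes per day from Week −5 to Week −1, before the quit date. The relevant loss is the 5% at TQD. With N = 304 and a 1-df noncentral F test (λ = f²·N), power is .97 at f² = .05 and about 1.00 at f² = .12. Even at N = 240 it would be .93 at f² = .05.

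**Step 5: what cannot be recomputed.** The Aim 1 gender interaction and the Aim 3 indirect effects were simulated with unpublished parameters. Fewer observed abstinence outcomes would lower their power, but by an unknown amount.

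**The case against.** Several points on the other side have force.

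- **No rate, and remedies followed.** The update was written mid-trial and gives no figure. Payments were shifted to follow-up (section 25.1 sets $75 per follow-up visit), surveys replaced reminder calls, and later text allows remote follow-up visits. Final retention for all 320 is unknown. This stands: the shortfall cannot be sized. What remains is that the inputs had not been met by 2019-11 and that no effect of the remedies on retention is stated.
- **Likelihood methods keep incomplete cases.** This is also true, but section 17.2 chose to compute power after attrition. Its word for that choice, conservative, contrasts discounting N with relying on missing-data methods. It makes no claim that 18% and 25% are pessimistic, so the word itself is not the defect. Nor would counting losses as smokers (a rule the plan does not state) restore power. If completers have control 25% and OR 2.3, multiplying both rates by (1 − loss) at N = 320 gives .81, .73 and .64 at 25%, 35% and 45% loss.
- **The primary EOT outcome is robust at OR 2.3.** This stands: power is still about .80-.82 at 40% loss.

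A reader might infer that every power statement in section 17.2 is undermined, or that the trial can no longer detect even its largest expected effect at 6M. The documents support neither. Aim 2 and the treatment and gender effects on the mediator rest on the 5% TQD figure, which the update does not dispute. At control 25%, OR 2.3 falls below .80 at 6M only once loss exceeds about 35%, and nothing in the protocol says that it did.

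**Conclusion.** The point holds for the EOT and 6M abstinence outcomes: Aim 1, its gender interaction and the Aim 3 indirect effects. It is an outdated planning input rather than a slip in arithmetic, since 262 and 240 follow correctly from 18% and 25%. The direction is clear for experience up to 2019-11, but the size is not. Under the stated assumptions, moving from the planned losses to 40% at EOT and 45% at 6M raises the smallest odds ratio with .80 power by about 0.25-0.3 at each visit, to roughly the top of the plan's expected range at EOT and above it at 6M.

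A separate and larger problem in section 17.2 is the lower end of the Aim 1 range. At OR 1.3, power is at most about .22 even with no attrition. Updating attrition does not resolve that, and narrowing the odds-ratio range while keeping N at 262 and 240 would not resolve this point.

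**What to change.** - In section 17.2, replace 18% and 25% with the loss observed to date at EOT and 6M, pooled over arms and blinded. If the retention measures are expected to help, give a stated range around it.
- Re-run the abstinence power for Aim 1 (including the gender interaction) and for Aim 3 at the resulting Ns, and state the smallest odds ratio with .80 power at each visit, with the control rates assumed.
- In section 10.1, mark the 82% and 75% retention figures as superseded. Leave the Aim 2 statement and the 5% TQD figure as they are.

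The cost is protocol wording and a re-run of existing power code. The stated power is likely to become less favourable. No extra enrolment, change of endpoint or change of analysis follows from this point.

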## 108        **1.0 Objectives**

109        *1.1 Describe the purpose, specific aims, or objectives of this research.*

110        Response:

111        Aim 1: Evaluate the impact of extended pre-quit varenicline therapy on smoking cessation.

112        Aim 2: Evaluate the impact of extended pre-quit varenicline therapy on smoking behavior and  
 113        related processes prior to cessation.

114        Aim 3: Evaluate the degree to which changes in pre-quit smoking behavior (Aim 2) truly account  
 115        for, or mediate, the impact of extended pre-quit varenicline on smoking cessation (Aim 1).

116        **UPDATE 2020-06-30 – OPTIONAL SALIVA SAMPLE FOR GENETIC ANALYSIS:** As detailed in  
 117        our administrative supplement request (EvarQuit Admin Supp Application – 2020-04-21.pdf), "...to  
 118        enhance this R01's ability to inform and link to precision medicine approaches, we propose to evaluate the  
 119        role of variants in two families of genes previously associated with varenicline concentrations, nausea,  
 120        and/or smoking cessation" (select SNPs related to drug transport [OCT2] and nicotinic receptor subunits  
 121        [CHRNA4/CHRN82]).

122        *1.2 State the hypotheses to be tested, if applicable.*

123        *NOTE: A hypothesis is a specific, testable prediction about what you expect to happen in your study*  
 124        *that corresponds with your above listed objectives.*

125        Response:

126        We hypothesize that extended run-in varenicline will improve bio-verified continuous abstinence  
 127        rates at end-of-treatment and at long-term follow-up (6- months), compared to the standard run-  
 128        in. Because extended pre-quit treatment may be particularly helpful for women (Becker et al.,  
 129        2008; [name] et al., 2012), the study is powered to evaluate moderation of treatment by gender.

130

131 Consistent with extinction theory, we predict that the extended run-in group will exhibit greater  
 132 pre-quit reductions in smoking (cigarettes per day, CO) than the standard run-in group. Effects  
 133 on other biological (cotinine, total nicotine exposure), self-report (subjective effects of smoking,  
 134 craving, withdrawal, nausea, expectancies), and behavioral (laboratory reinforcement task)  
 135 outcomes will also be evaluated to better characterize potential treatment mechanisms.

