206 allow greater repeated natural exposure to attenuated reinforcement from smoking prior to the target quit  
207 date (TQD). We recently tested this approach in small-RCTs of both bupropion ([name] et al., 2015 /Prelim  
208 Study 1) and varenicline ([name] et al., 2012 / Prelim Study 2; see also Ashare et al., 2012, Gass et al.,  
209 2012); treatment-seeking smokers were randomized to either a Standard run-in group (3 weeks of placebo,  
210 1 week of pre-TQD medication) or an Extended run-in group (4 weeks of pre-TQD medication); all  
211 participants received counseling and typical regimens of post-TQD medication. Hajek et al. (2011)  
212 conducted an independent but very similar small-scale RCT of varenicline. In all three pilot RCTs, the  
213 results were consistent with an extinction hypothesis: the extended run-in resulted in greater reductions in  
214 smoking rate (and tended to reduce craving and smoking satisfaction) prior to the TQD and improved  
215 abstinence rates at short-term follow-up. (In both [name] et al. studies, there was evidence that the extended  
216 run-in had a greater impact among women more than men; Hajek et al. did not examine gender effects).  
217 Overall, the results of these three studies are promising, particularly because the control condition was an  
218 approved cessation medication; in the case of varenicline, the extended run-in beat the current “best in  
219 class” treatment (standard run-in varenicline). However, the studies were limited by their small sample  
220 sizes (Ns=60-100) and short-term follow-up (4 weeks – 3 months).

221 The proposed study takes the next critical step in evaluating the degree to which extended-run in  
222 varenicline will set a new efficacy standard in smoking cessation, a large-scale RCT with long-term follow-  
223 up. Thus, the primary significance of the proposed RCT is that it will, if successful, provide a marked  
224 advance in the treatment of cigarette smoking, the leading preventable cause of death in the US. Moreover,  
225 it would do so at far less cost and far more quickly than traditional pharmaceutical development pathways  
226 (see Chong & Sullivan, 2007; Collins, 2011). Although every innovation in treatment faces challenges in  
227 bridging the science-practice gap, the proposed treatment and RCT are designed to facilitate and inform  
228 widespread dissemination and implementation (see the Introduction to the revision), further enhancing the  

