265 Response: Participants will be 320 treatment-seeking adult smokers (160 female).

266

267 **UPDATE 2020-06-30 – OPTIONAL SALIVA SAMPLE FOR GENETIC ANALYSIS:** An optional  
 268 saliva sample for genetic analysis will be obtained from up to 200 of the 320 participants.

269 **5.2 If applicable, indicate how many subjects you expect to screen to reach your target sample (i.e. your  
 270 screen failure rate).**

271 Response: To accrue 320 ITT participants across 44 months, we have developed conservative projections  
 272 for accruing 9 ITT participants per month: screening approximately 55 potential participants by phone each  
 273 month, with 50% (28) of those eligible after phone prescreen, 50% (14) of those attending the intake visit,  
 274 75% (10) of those at intake consenting and remaining eligible after full screening, and 90% (9) of those  
 275 eligible ultimately achieve ITT status.

276 **2019-11 Update (approved/implemented early 2020-01):** In recent months, we have extensively  
 277 reviewed our accrual process. Accrual flow projections that we made in the grant proposal (e.g., 50%  
 278 eligible on phone screen, 75% eligible at intake visit) have been accurate, with one critical exception. We

279 predicted that we would lose no more than 10% of prospective participants between the intake visit and  
 280 beginning treatment 1-2 weeks later (and counting as one of our 320 intent-to-treat, or ITT, participants). In  
 281 reality, we have lost more than twice that many people (21%) at this stage. Importantly, the loss of potential  
 282 participants between the intake visit and ITT disproportionately affects the representation of racial/ethnic  
 283 minorities. That is, participant loss at this stage is 36% for people from minorities compared to 15% for  
 284 non-Hispanic Caucasians.

285 In an effort to improve the proportion of intake-eligible participants who ultimately achieve ITT status,  
 286 we made the following changes with the 2019-11 IRB modification:

- 287 1. Increase remuneration for the lab visits (see Section 26.1), which provide no clinical benefit and last  
 288 longer than clinic visits.
- 289 2. Eliminate the 50% adherence requirement for the device-initiated assessments in the Ecological  
 290 Momentary Assessment (EMA; see section 11.1).

291  
 292 5.3 *Justify the feasibility of recruiting the proposed number of eligible subjects within the anticipated  

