 683 the post-quit period: increased frequency of payment (from once every two weeks to three times per week)  
 684 and increased amount of payment (from \$1/assessment to \$2/assessment).

685 In order to complete the EMA SWAT, over the course of a one-year period participants (equal  
 686 numbers of male and female, and of Caucasian and African-American) will be randomly assigned to each  
 687 of three conditions in advance of the TQD until we accrue 20 participants in each condition. At the TQD,  
 688 participants in the SWAT will receive a written consent addendum.

689  For the three versions of the addendum, see EvarQuit Addendum – EMA SWAT – 2018-12-06.doc.

690 Participants randomly assigned to the standard condition would simply be informed that it is  
 691 important to continue the EMA over the next four weeks. Participants randomly assigned to the increased  
 692 frequency of payment and increased amount of payment will have the opportunity to accept or decline the  
 693 modified payment plan. If they decline, they will simply continue to participate in EVarQuit, but will be  
 694 not be enrolled in the SWAT.

695 We chose individualized addenda over a single broad consent form because the SWAT will only  
 696 pertain to a subset of EVarQuit participants. We considered explaining all three conditions to SWAT

697 participants, but ultimately decided against it because doing so could cause unnecessary distress to  
 698 participants randomized to the standard condition (who might feel they were 'losing out' even though  
 699 nothing had changed).

700 The results of the SWAT will inform our decision of whether to alter remuneration for subsequent  
 701 participants in the EVarQuit project.

702 *Clinic visits (Weeks -4, -3, -1, 0 [TOD], 2, and 4), randomization, and study medication.* At Clinic  
 703 Visit 1 (Week -4), participants are randomized (within gender) to the extended or standard run-in group,  
 704 complete study measures (see below), receive brief behavioral counseling (see below) and study  
 705 medication (details below), and are instructed to begin the medication the next day. Subsequent study visits  
 706 are similar in process and content. *Randomization.* The study statistician (Co-I [name]) will implement  
 707 and monitor the small-urn randomization (within-gender in urns/blocks of 8 [4 extended run-in, 4 standard  

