 1337 interactions in Aims 1 and 2 and all effects in Aim 3, we estimated power using Monte Carlo simulations  
 1338 estimated in Mplus (Muthén, & Muthén, 2002) with 10,000 replications and parameters taken from our  
 1339 pilot study ([name] et al., 2012). Our monte carlo simulation suggested adequate power to detect the  
 1340 proposed gender x treatment interactions, with minimal bias in the regression coefficients and  
 1341 corresponding standard errors (bias  $< 3\%$ ). For Aim 3, our Monte Carlo simulation suggested adequate  
 1342 power to detect the proposed mediational pathway (collapsing across gender) with minimal bias in the  
 1343 estimated indirect effect and corresponding standard error (bias  $< 2\%$ ). Furthermore, our Monte Carlo  
 1344 simulation suggested adequate power to detect the gender x treatment interaction predicting the proposed  
 1345 mediator, and the proposed indirect effect for women with minimal bias for these effects and the  
 1346 corresponding standard errors (bias  $< 1\%$ ). Hence, we have adequate power to detect moderated mediation.  
 1347 Please note that our power calculations are unusually strong in that all effect size estimates were based on  
 1348 existing data, rather than hypothetical estimates, which we believe provides greater confidence in our  
 1349 calculations.

1350 **17.3 Describe any procedures that will be used for quality control of collected data.**

1351 Response: As part of the data and safety monitoring process, the team will ensure that all fields are  
 1352 completed appropriately, and all corrections are done according to Good Clinical Practice (GCP). Any  
 1353 inconsistencies/ deviations will be documented. The Study Physician will review inclusion/exclusion data  
 1354 for each participant, documenting reviews of each report. The Project Manager will conduct quality control  
 1355 reviews of data on an on-going basis.

1356

1357 **18.0 Confidentiality**

1358

1359 **A. Confidentiality of Study Data**

1360

1361 *Describe the local procedures for maintenance of confidentiality of study data and any records that will be*  
 1362 *reviewed for data collection.*

1363

1364 **18.1 A. Where and how will all data and records be stored? Include information about: password**  
 1365 **protection, encryption, physical controls, authorization of access, and separation of identifiers and data, as**  
 1366 **applicable. Include physical (e.g. paper) and electronic files.**

1367

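### The moderated-mediation power in 17.2 does not follow from what was simulated, and the Aim 1 gender-interaction claim holds only for a very large gender difference that the protocol does not state

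*Combined protocol and SAP*

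**What the plan says.** Section 1.2 states without condition that "the study is powered to evaluate moderation of treatment by gender". Section 17.2 sets the standard: "alpha level of .05 and adequate power considered" at .80 or above. For the main effect of run-in group, with power from Proc Power, it says "effect sizes are expected to be in the range of small to medium for Aim 1 (Odds ratios 1.3 to 2.3) and Aim 2".

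The gender interactions in Aims 1 and 2, and everything in Aim 3, were handled separately: a Mplus Monte Carlo study with 10,000 replications and parameters from the investigators' pilot. From it the section reports adequate power for the "proposed gender x treatment interactions, with minimal bias in the regression coefficients and" standard errors. For Aim 3 it reports adequate power for the gender interaction on the mediator and for the indirect effect in women, and concludes: "Hence, we have adequate power to detect moderated mediation".

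The section prints no interaction effect size, gender-specific odds ratio, standard-arm abstinence rate or numerical power. Section 3.1 describes the pilot trials as limited by small sample "sizes (Ns=60-100) and short-term follow-up".

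**The concern.** There are two separate problems.

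First, moderated mediation means that the indirect effect differs between women and men. Section 17.1 asks exactly that for Aim 3. An indirect effect can be detectable in women without being distinguishable from the men's, and a detectable interaction on the mediator is only one of the two paths involved. The concluding sentence therefore claims power for a quantity whose power is not reported.

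Second, interactions on a binary outcome with 80 per cell are estimated imprecisely. If .80 power requires an extreme gender difference, an unconditional statement that the trial is powered for moderation gives readers no way to judge what a non-significant interaction means. It could then be mistaken for equal benefit in men and women.

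**Working it through.** **Plan's own figure.** Only the threshold of .80 is printed. Without the pilot parameters the simulated power cannot be reproduced.

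**A. Moderated mediation**

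Let a_w and a_m be the treatment effects on the mediator in women and men, a3 = a_w − a_m, and b the mediator's effect on abstinence. I take b as common to both genders, since 17.2 places the gender interaction on the mediator. The women's indirect effect is a_w·b. The difference in indirect effects is a3·b, the index of moderated mediation. Under the joint-significance approximation:

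- power(women's indirect) ≈ power(a_w) × power(b)
- power(index) ≈ power(a3) × power(b) = power(a3) × power(women's indirect) / power(a_w)

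Power of .80 for a3 means a standardised effect of 1.96 + 0.84 = 2.80. If a_m = 0, then a_w = a3 with a standard error smaller by √2, so its standardised effect is 2.80 × 1.414 = 3.96 and power(a_w) = Φ(3.96 − 1.96) = .977. If men also respond, power(a_w) is closer to 1. This gives:

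| power(a3) | power(women's indirect) | power(index) |
|---|---|---|
| .80 | .80 | .80 × .80 = .64, up to .64/.977 = .66 |
| .80 | .85 | .80 × .85 = .68, up to .68/.977 = .70 |
| .90 | .90 | about .81 |
| .90 | .95 | about .86 |

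**B. Aim 1 gender interaction**

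Inputs from the protocol: "Participants will be 320 treatment-seeking adult smokers (160 female"); "and monitor the small-urn randomization (within-gender in urns/blocks of 8 [4 extended run-in, 4 standard" run-in], hence 80 per gender-by-arm cell; alpha .05; attrition of 18% at end of treatment (262 left, 65.6 per cell) and 25% at 6 months (240 left, 60 per cell); logistic regression with a gender x treatment term.

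Assumptions: a two-sided test (sidedness is not stated), and standard-arm abstinence of 20% to 50%, equal in men and women. The only anchor in the documents is the 1 in 4 long-term rate in 3.1.

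Formulas: SE = √[Σ 1/(n p(1−p))] over the four cells; power = Φ(|ln ratio|/SE − 1.96).

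*Best case, every cell at 50%.* No baseline rate is assumed here, because this is the smallest possible SE. SE = √(16/n), and the ratio for .80 power is exp(2.80 × SE).

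- N=320: SE = √(16/80) = 0.447, ratio 3.5
- N=262: SE = √(16/65.6) = 0.494, ratio 4.0
- N=240: SE = √(16/60) = 0.516, ratio 4.2

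*Men's OR 1.0, with a worked case at a 30% standard-arm rate and N=320.* Women's OR 3.85 gives 62.3% in their extended arm. Three cells contribute 1/(80 × .3 × .7) = .0595 each and the fourth .0532. SE = √.2318 = 0.481, ln 3.85 = 1.348, 1.348/0.481 = 2.80, and power is .80.

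| | N=320 | N=262 (EOT) | N=240 (6M) |
|---|---|---|---|
| Ratio for .80 power, best case | 3.5 | 4.0 | 4.2 |
| Ratio for .80 power, men's OR 1.0, rates 20–50% | 3.7–4.5 | 4.3–5.2 | 4.6–5.6 |
| Power at men's OR 1.3, women's 2.3 (illustration) | 19.1–24.2% | 16.5–20.7% | 15.5–19.3% |

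*Fit with the main-effect range.* Hold the geometric mean of the two gender-specific ORs at 1.3 to 2.3 and solve for .80 power at N=320. The ratio is 3.6 to 4.9, with men's OR 0.59 to 1.19 and women's 2.5 to 4.8. For example, a mean of 1.73 at a 30% rate gives men 0.88, women 3.40, ratio 3.87.

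*How well a pilot fixes such a ratio.* With 60 to 100 participants split evenly, there are 15 to 25 per cell. Even in the best case, SE = √(16/15) = 1.03 to √(16/25) = 0.80, so 95% limits lie a factor of exp(1.96 × 0.80) = 4.8 to exp(1.96 × 1.03) = 7.6 either side of the estimate.

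**The case against.** The strongest reply is that the interaction was powered by its own simulation from pilot data, not from the main-effect range. Benefit concentrated in women is what the protocol hypothesises and what it reports from its pilots. Gender-specific ORs that reach .80 do fit inside the stated average range, as shown above. The parameters may also be in the attached grant application, which is not available here. All of this stands: the Aim 1 claim is uncheckable from the protocol, not shown to be wrong.

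A reader might infer that the design has only 15% to 24% power under the protocol's own assumptions. The documents do not support that. The range 1.3 to 2.3 is given for the main effect of run-in group, and no section assigns its ends to men and women; the figure illustrates one possible gender difference. Nor is 3.7 an absolute minimum ratio: it depends on men's OR being 1.0, and the best-case limit is 3.5.

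A reader might also extend the point to the Aim 2 interaction. That mediator is continuous, and nothing here tests the claim about it.

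On mediation, adequate means at least .80, so the components may have been well above it and the index could reach .80. That is fair, but the protocol gives neither component's value, and the conclusion is worded as following from adequacy alone.

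**Conclusion.** The inference to moderated mediation is invalid as written. Components that just meet the protocol's threshold imply about .64 for the difference in indirect effects, and .80 with .85 implies about .70. This rests on the joint-significance approximation, a b path common to both genders, and extended run-in not lessening smoking reduction in men. The logical gap itself needs none of these assumptions.

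The Aim 1 interaction claim is not refuted. It can hold only if the ratio of odds ratios is at least 3.5, 4.0 and 4.2 at N=320, end of treatment and 6 months, and more plausibly 3.7–4.5, 4.3–5.2 and 4.6–5.6 under the stated assumptions. At N=320, with an average OR of 1.3 to 2.3, that means little benefit or harm in men (OR about 0.6–1.2) and a large benefit in women (about 2.5–4.8). A smaller but still substantial difference would usually be missed. The unconditional statement in 1.2 should be qualified. The Aim 2 interaction claim is unaffected.

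**What to change.** 1. In 17.2, replace the concluding sentence on moderated mediation with the simulated power for the difference in indirect effects (the index of moderated mediation), together with the path values used. If it is below .80, restate the claim.
2. In 1.2 and 17.2, qualify the Aim 1 moderation claim with the ratio of odds ratios detectable at .80 power at N=320, end of treatment and 6 months. Print the pilot interaction value and the standard-arm rates assumed.
3. Keep the prespecified interaction test, and report gender-specific odds ratios and their ratio with 95% CIs beside it. State that a non-significant interaction is not evidence of equal effect.

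The cost is wording and one simulation in a model already built, with no added participants. The stated power becomes less favourable.
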